Cover Page

Official title of the study: Coil Hysteroscopic Tubal Occlusion,
the Treatment of Hydrosalpinx Before IVF-ET

Date: 12/01/2015

Study protocol

The problem to be investigated

Project title: Coil Hysteroscopic Tubal Occlusion, the Treatment of Hydrosalpinx Before IVF-ET

Research problem: This will be an investigation to evaluate the success rate of proximal tubal occlusion with coil devices in women with hydrosalpinx and to observe the pregnancy rate with IVF-ET.

Background: Many studies have proposed that hydrosalpinx fluid may decrease the pregnancy rate following IVF-ET (Zeyneloglu HB, 1998; Strandell A, 1999; Nackley AC, 1998).

During nearly two decades, researchers have find many treatments to improve the outcomes of IVF-ET with hydrosalpinx, such as fluid extraction, salpingectomy, proximal tubal occlusion with Essure device (HTO-E) and other devices (D'Arpe S, 2015; Lorente Gonzalez J, 2016;). However, extraction cannot prevent the refluxing of fluid which may directly poison the embryos while salpingectomy may decrease the ovarian response. Laparoscopic salpingectomy may increase the risk for patients who have had a history of severe pelvic adhesions. Besides, proximal tubal occlusion with Essure have been demonstrated to be companied by some severe

complications (Walter JR, 2017). Therefore, another safer device should be investigated. Fibered platinum coils have been used in aneurysm and endovascular therapy more than a decade ago (Tsai CW, 1996). However, with wide usage, the complication was few (Syha R, 2016).

The aims: The aim of our study was to evaluate the successful and complication rate after occlusion with fibered platinum coils, and to observe the pregnancy rate following IVF-ET.

(v) The hypothesis: Hysteroscopic occlusion will be an alternative to the treatment of hydrosalpinx before IVF-ET.

2. Methods of investigation:

Subjects: 80 females between 20-45 years old with unilateral or bilateral hydrosalpinx as confirmed by HSG.

Inclusion criteria:

1. Have unilateral or bilateral hydrosalpinx as evidenced by HSG.
2. Laparoscopic surgery was considered to be contraindicated because of suspected extensive pelvic adhesions.
3. Patients are willing to undergo a hysterosalpingogram (HSG) 3 months after tubal occlusion.
4. Patients are willing to participate in this clinical study.
5. Patients are able to comprehend and give informed consent

for participation in this study.

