Cover Page

Official title of the study: Coil Hysteroscopic Tubal Occlusion,
the Treatment of Hydrosalpinx Before IVF-ET

Date: 12/01/2015

Statistical Analysis Plan

1. Measurements used: Successful placement of coils will be judged by the correct placement that confirmed by vaginal ultrasound examination. Implantation rate, first-trimester spontaneous miscarriage rate and on-going pregnancy rate will also be calculated.
2. Sample size calculation: As a single-arm trial, 80 females will be recruited in our study.
3. Statistical methods: Data analysis was performed with SPSS version 22.0 (SPSS, Inc., Chicago, IL, USA), using two-sided test, and a p value < 0.05 was considered statistically significant. The participants who received insertion of fibered coils were followed up and the outcomes were recorded. Chi-square test will be applied to evaluate the basic data of the participants including age and IVF-ET cycles. Ratio was applied in the outcomes of miscarriage rate and pregnancy rate.

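### The SAP plans no analysis of two protocol aims, HSG-confirmed tubal occlusion and complications, and gives its IVF rates without intervals or settled denominators

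*SAP*

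**What the plan says.** **Protocol.** The research problem is to "evaluate the success rate of proximal tubal occlusion with coil devices in women with hydrosalpinx and to observe the pregnancy rate with IVF-ET". The aims section adds safety: "The aim of our study was to evaluate the successful and complication rate after occlusion with fibered platinum coils". Under Experimental procedure, a vaginal ultrasound on the third day after surgery checks coil position. An HSG at 3 months checks that the tubes are closed, and IVF-ET follows. Disease may be on one side or both (inclusion criterion 1). Entry is limited to women for whom laparoscopy is considered contraindicated (criterion 2) and who are willing to have the 3-month HSG (criterion 3).

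**SAP 1, Measurements used.** "Successful placement of coils will be judged by the correct placement that confirmed by vaginal ultrasound examination". Then: "Implantation rate, first-trimester spontaneous miscarriage rate and on-going pregnancy rate will also be calculated". HSG and complications do not appear here or elsewhere in the SAP.

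**SAP 2, Sample size calculation.** "As a single-arm trial, 80 females will be recruited in our study". No rate, precision target or allowance for drop-out is given.

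**SAP 3, Statistical methods.** For the IVF outcomes: "Ratio was applied in the outcomes of miscarriage rate and pregnancy rate". On who is analysed: "The participants who received insertion of fibered coils were followed up and the outcomes were recorded". On baseline data: "Chi-square test will be applied to evaluate the basic data of the participants including age and IVF-ET cycles".

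**The concern.** In a single arm with no outcome test, the estimates and their uncertainty are the whole result. Three things are missing.

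1. **The lead question has no planned analysis.** Coil position on ultrasound and tubal closure on HSG are separate steps in the protocol. A placement rate does not answer a question about occlusion. Complications are an aim, and the background section justifies coils on safety grounds, yet no complication rate is planned.
2. **No interval is planned for any rate.** A reader would get percentages with no indication of how far they could be from the truth.
3. **The denominators are not settled.** HSG and IVF-ET come after insertion, so fewer women may contribute to the later rates. The follow-up sentence in SAP 3 covers women who received coils. It does not say what happens to women whose insertion failed, who miss the HSG or who never reach transfer. With bilateral disease, a woman with one of two tubes closed could be counted as a success or a failure.

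The headline percentage could therefore be settled after the data are seen.

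**Working it through.** **The plan's own figure.** The only number is 80 women. It cannot be reproduced, because SAP 2 gives no inputs.

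**Aims set against analyses.**

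| Quantity | Protocol | SAP |
|---|---|---|
| Coil placement (ultrasound) | scheduled | measured; no interval |
| Tubal occlusion (3-month HSG) | lead question; scheduled | absent |
| Complications | stated aim | absent |
| Pregnancy | to be observed after IVF-ET | ratio; no interval |
| Miscarriage | not named | ratio; no interval |
| Implantation | not named | to be calculated; no interval |

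**Illustration.** Only the 80 is from the documents. All other counts below are assumed, including that insertion is attempted in all 80 women. Intervals are Clopper-Pearson: for x events in n, the lower limit is the 2.5% quantile of Beta(x, n−x+1) and the upper limit is the 97.5% quantile of Beta(x+1, n−x).

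*Denominator for pregnancy, 24 pregnancies*
- 24/80 = 30.0% (20.3-41.3%)
- 24/60 = 40.0% (27.6-53.5%), if 60 women reach IVF-ET

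*The same over a range of attrition, 28 pregnancies*
- 28/80 = 35.0% (24.7-46.5%)
- 28/76 = 36.8% (26.1-48.7%)
- 28/68 = 41.2% (29.4-53.8%)
- 28/60 = 46.7% (33.7-60.0%)

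*Denominator for occlusion, 63 women with confirmed occlusion*
- 63/80 = 78.8% (68.2-87.1%)
- 63/70 = 90.0% (80.5-95.9%), if 70 women have an HSG

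*Woman or tube.* Take 40 unilateral and 40 bilateral cases: 40 + 2×40 = 120 tubes. With 12 tubes not occluded, the per-tube rate is 108/120 = 90.0%. The per-woman rate (every treated tube closed) depends on where the failures fall:
- 12 failures in 12 women: (80−12)/80 = 68/80 = 85.0% (75.3-92.0%)
- both tubes in 6 women: (80−6)/80 = 74/80 = 92.5% (84.4-97.2%)

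*Complications.* With 0 in 80, the upper limit is 1 − 0.025^(1/80) = 4.5%.

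*Miscarriage per pregnancy.* 4/24 = 16.7% (4.7-37.4%).

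*Largest half-width of a per-woman interval.* It is 11.4 points with 80 women (40/80: 38.6-61.4%) and 13.2 with 60 (30/60: 36.8-63.2%).

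*Clustering.* Assume implantation at 30% with 2 embryos in each of 60 women. The half-width is 1.96 × √(0.3×0.7/120 × [1 + (2−1)ρ]), which is 8.2 points at within-woman correlation ρ = 0 and 10.0 points at ρ = 0.5. The effect is modest.

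**The case against.** The best defence is that this is a small descriptive study. It needs no test, no comparator and no success threshold, and 80 women can serve its aim. That stands, and nothing here asks for a test or more patients. Several stronger readings are tempting but are not supported.

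- **That the pregnancy rate has no denominator at all.** The protocol speaks of the patients' pregnancy rate and places it after IVF-ET, which points to a per-patient rate. What remains open is how women who never reach IVF-ET are counted, and whether the rate is first-cycle or cumulative.
- **That the baseline chi-square is impossible in one arm.** Groups can exist within an arm, for example unilateral and bilateral disease. The SAP simply names none, so the meaning of a p-value is undefined.
- **That the hypothesis makes a comparative claim it cannot support.** Criterion 2 limits entry to women judged unsuitable for laparoscopy, so calling the procedure an alternative may mean only that it is an option for them. No benchmark is given, so the data support estimation only.
- **That many women will miss the HSG.** Criterion 3 requires willingness to have it. The 70 above is an assumption, not a forecast.

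It can also be said that readers can work out intervals for themselves. That is true for per-woman rates if counts are published. It is not true for per-tube or per-embryo rates, because totals hide clustering within women. Nor can a reader recover a denominator that was never fixed in advance.

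**Conclusion.** The point holds, and the SAP should be amended. Two protocol aims, occlusion and complications, have no planned analysis, and the SAP's placement criterion does not stand in for occlusion. No rate has a planned interval. The counting of women who drop out before HSG or IVF-ET, and the unit for occlusion, are undefined.

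In the illustrations, the choice of denominator alone moves pregnancy by 10 points (30.0% to 40.0%) and occlusion by about 11 (78.8% to 90.0%). These sizes rest on assumed counts: with less attrition the shift is smaller (28 pregnancies: 35.0% of 80, 36.8% of 76). The omissions themselves rest on the text and need no assumption.

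The unnamed chi-square groups and the missing benchmark for the hypothesis are minor matters of wording. None of this makes the single-arm design unsuitable for description.

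**What to change.** In SAP 1, add HSG-confirmed occlusion and complications as analysed outcomes. The sponsor needs to state which events count as complications and over what period. In SAP 3, replace the ratio sentence with:

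> All per-woman rates are reported as n/N with an exact (Clopper-Pearson) 95% CI. The main denominator for placement, complications, HSG-confirmed occlusion, pregnancy and ongoing pregnancy is all women in whom insertion was attempted. Occlusion success means that every tube in which insertion was attempted is occluded on the 3-month HSG; a failed insertion or no HSG counts as not confirmed. Supporting rates are occlusion among women with an HSG and per tube, and pregnancy per woman reaching IVF-ET, with first-cycle and cumulative pregnancy shown separately. Miscarriage is per pregnant woman. Per-tube and per-embryo intervals allow for clustering within woman.

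A bootstrap that resamples women would serve for the clustered intervals.

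Replace the baseline chi-square with descriptive summaries, or name its groups (for example unilateral versus bilateral). State in the protocol that the study estimates these rates in women for whom laparoscopy is considered contraindicated, without a comparative claim.

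**Cost.** The changes are to wording, with no extra patients, visits or procedures, since the ultrasound and HSG are already planned. Results must be recorded per tube as well as per woman. The headline rates may be lower than on a reduced denominator, and the intervals will be visibly wide, up to about ±11.4 points with 80 women.

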6. Have read, understood and signed an informed consent form.

Exclusion Criteria:

Active or recent upper or lower pelvic infection

Known hypersensitivity to nickel as confirmed by skin test

Known allergy to contrast media pregnancy or suspected pregnancy

Poor general or gynecologic health

Inability or refusal to provide informed consent

Design: subjects who meet the inclusion and exclusion criteria will be eligible, all the eligible subjects will be interviewed and the purpose of the trial will be outlined. Epidemiologic data will also be collected.

Experimental procedure: hysteroscopic tubal occlusion will be performed in the 3-7days after the menses. In the third day after the surgery, a vaginal ultrasound will be performed to confirm the position of coil. 3 months later, HSG will be taken out to confirm the occlusion of tubes. After the treatment, IVF-ET will be applied and then the patients' pregnancy rate will be assessed in the following-up.

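### Does the pregnancy rate need a stated unit, denominator and time window before it can be reported?

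*SAP*

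**What the plan says.** Observing pregnancy after IVF-ET is one of the aims in the protocol, beside the success and complication rates of the occlusion. The hypothesis is "Hysteroscopic occlusion will be an alternative to the treatment of hydrosalpinx before IVF-ET". Under Experimental procedure the protocol says "After the treatment, IVF-ET will be applied" and that the "pregnancy rate will be assessed in the following-up". It sets no number of cycles and no end of follow-up.

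The SAP's Measurements used item deals first with successful coil placement and then adds "Implantation rate, first-trimester spontaneous miscarriage rate and on-going pregnancy rate will also be calculated". Its Statistical methods item contains three relevant sentences:

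- on who is followed: "The participants who received insertion of fibered coils were followed up and the outcomes were recorded";
- on baseline description: "Chi-square test will be applied to evaluate the basic data of the participants including age and IVF-ET cycles";
- on the outcomes themselves: "Ratio was applied in the outcomes of miscarriage rate and pregnancy rate".

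The study has a single arm of 80 women. No expected pregnancy rate, reference rate or precision target is given.

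**The concern.** A pregnancy rate in an IVF setting can be computed per woman, per started cycle or per transfer. It can also be taken over all enrolled women, coil recipients or women who reached a transfer. The plan does not choose. If women have differing numbers of transfers over an open follow-up, a per-woman cumulative rate rises with the number of attempts even when the chance per transfer is constant. A rate among women with a transfer leaves out those who never got that far.

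With no control arm, the figure can be read only against outside rates, and such a comparison needs a known unit and denominator. An unfixed denominator also leaves room to choose the most favourable one after seeing the data. At stake are the comparability and interpretation of a descriptive estimate. No type I error rate or power is affected, because no test of pregnancy is planned.

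**Working it through.** **What can be reproduced.** The plan gives no figure for pregnancy, and N = 80 comes without inputs, so there is no planned number to recompute. Apart from N = 80, all inputs below are assumptions.

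**Effect of attempts.** Let p be the chance of ongoing pregnancy per transfer and k the number of transfers, with independent transfers and stopping at the first success. The per-woman rate is 1 − (1 − p)^k.

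| p | k = 1 | k = 2 | k = 3 |
|---|---|---|---|
| 20% | 20.0% | 36.0% | 48.8% |
| 30% | 30.0% | 51.0% | 65.7% |
| 40% | 40.0% | 64.0% | 78.4% |

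Suppose instead that women differ in their chance, following a beta distribution with mean 30% and within-woman correlation 0.1 (a = 2.7, b = 6.3). The rates are then 30.0%, 1 − 0.700 × 0.730 = 48.9%, and 1 − 0.700 × 0.730 × (8.3/11) = 61.4%. The rise does not depend on independence.

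It does depend on the measure. In the simple model with p = 30%, 80 women and up to three transfers, 52.6 pregnancies are expected from 175.2 transfers, and 52.6/175.2 = 30.0%. The per-transfer rate is unchanged by attempts, and so is a first-transfer rate.

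**Effect of the denominator, one transfer each.**

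| Scenario (assumed) | Enrolled | Coil recipients | Women with a transfer | Spread |
|---|---|---|---|---|
| 19 pregnancies | 19/80 = 23.8% | 19/76 = 25.0% | 19/64 = 29.7% | 5.9 points |
| 17 pregnancies | 17/80 = 21.3% | 17/72 = 23.6% | 17/56 = 30.4% | 9.1 points |

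**Scale against sampling error.** The exact (Clopper-Pearson) 95% interval for 19/80 is 14.9% to 34.6%, and for 17/80 it is 12.9% to 31.8%. The highest alternative figure in each row (29.7% and 30.4%) lies inside the interval for the enrolled denominator. This comparison gives scale only: a change of denominator is a change in what is estimated, not random error.

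**Worst combination.** With p = 30%, the rate per enrolled woman after one transfer, if 70% reach transfer, is 0.70 × 30% = 21.0%. The rate per transferred woman after up to three transfers is 65.7%. The gap of about 45 points stacks extreme choices on attempts, denominator and share reaching transfer, so it is a ceiling.

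**What the text narrows.** The sentence on follow-up of coil recipients stands directly before the analyses and says that their outcomes are recorded, so the natural reading is that they are the analysed group. Naming first-trimester miscarriage beside ongoing pregnancy suggests that ongoing means beyond the first trimester. The listing of "basic data of the participants including age and IVF-ET cycles" does not settle the unit, since it may refer to earlier cycles.

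**The case for a change.** The strongest case for a change is that pregnancy is a stated aim, the hypothesis presents occlusion as an alternative treatment, and a single-arm rate means little unless its unit and denominator are known. Fixing them beforehand costs a few sentences in the SAP and removes the chance of choosing after the data are seen. The sentence about coil recipients names who is followed without tying the rate to them, and read as a denominator it leaves out failed placements.

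Much of this stands. The unit, cycle limit, window and gestational week are not written down, and a written definition would be better practice. Two things weaken it as a case for change.

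First, there is no single correct definition to move to. First transfer or cumulative, and all enrolled, recipients or transferred, are choices on which experienced statisticians differ. An all-enrolled rule that counts no transfer as not pregnant brings its own difficulties. The SAP describes follow-up only of coil recipients, so a woman whose placement failed but who went on to IVF-ET might have no recorded outcome, and losses to follow-up would still need a rule.

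Second, the difficulty of attributing the figure to the treatment comes from the absence of a control arm and would remain under any denominator.

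**Conclusion.** No change to the plan is needed. This is missing detail in a descriptive outcome: no stated rule is wrong and no planned figure is off. The analyst must choose a numerator and a denominator to report any proportion. Coil recipients are the group the SAP points to, and a report that shows counts, denominators and transfers per woman gives a reader what is needed.

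Under assumed single-transfer inputs the choice moves the rate by about 6 to 9 points, no more than the sampling uncertainty at 80 women. The larger movement, from 30% to 51% or 65.7%, arises only if women have two or three transfers and the rate is reported cumulatively per woman. The documents state neither. If follow-up did include repeated transfers and a single cumulative percentage were published without counts, the reader would be poorly served. That would be a fault of the report, and nothing in the plan requires it.
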